**Academic Position: Lecturer**

**Department: Anesthesia, Intensive Care and Pain Management**

## **What is already known on this subject? AND**

## **What does this study add?**

Intra-abdominal infections are a major cause of morbidity and mortality in hospital settings worldwide. However, data from most published clinical trials underestimate the true mortality risk for several reasons. (Meng et al., 2024).

Major surgery may induce an inflammatory response, which results in an increased level of C-reactive protein (CRP) and represents in albumin loss to the extravascular area due to increased capillary permeability. Our study will be done to evaluate the association between capillary leak index (CLI) and intensive care unit related mortality in patients underwent major abdominal surgery (Susanti et al., 2021).

## **1. INTRODUCTION**

Sepsis has been recognized as a life-threatening organ dysfunction caused by a dysregulated host response to infection (Clements, 2021). Considerable advances have since been made into the pathobiology (changes in organ function, morphology, cell biology, biochemistry, immunology, and circulation), management, and epidemiology of sepsis, suggesting the need for continuous research (JAMA, 2016).

Peritonitis can be classified by the anatomical integrity of the abdominal cavity. Primary peritonitis is associated with undamaged intra-abdominal cavity organs. It is also known as spontaneous bacterial peritonitis and is treated without surgical intervention. The source of infection is often hard to establish and is usually found occurring in infants and cirrhotic patients (Mureşan et al., 2018).

Secondary peritonitis is an infection of the peritoneal cavity after hollow viscus perforation, anastomotic leak, ischemic necrosis, or other injuries of the gastrointestinal tract (Montravers et al., 2015). Tertiary peritonitis is defined as a serious recurrent or persistent intra-abdominal infection after the successful control of secondary peritonitis. Irrespective of the cause, several measures are available and accepted as improving the survival rate, the most important being the early recognition of intra-abdominal infection. Efforts to achieve fluid balance should be initiated immediately to replace any intravascular insufficiency. Vasoactive agents

may be necessary to augment and assist fluid restoration (Vincent JL and De Backer 2013). The treatment strategy for peritonitis primarily aims at the stabilization of possible organ dysfunction by routine intensive care medicine. Low risk secondary peritonitis (localized peritonitis), Ampicillin/Sulbactam or Carbapenem can be used as a monotherapy, however in combination therapy 2nd generation Cephalosporin + Metronidazole or 3rd generation Cephalosporin + Metronidazole can be used (Sartelli et al., 2016). High risk Secondary peritonitis Piperacillin/Tazobactam or Carbapenem or Tigecycline can be used as a monotherapy. A combination therapy 4th generation Cephalosporin + Metronidazole are usually used. Tertiary peritonitis antifungal therapy in high-risk patients and empirical therapy should cover the probable micro flora and should be changed according to the culture results (Morrissey et al., 2013).

Capillary leak syndrome (CLS) refers to a syndrome of deranged fluid homeostasis, often observed in critically ill patients, CLS is frequently defined by excessive fluid shift from the intravascular to the extravascular space, resulting in intravascular hypovolemia, extravascular edema formation, and hypo perfusion necessitating further fluid resuscitation. In health, fluid exchange between intravascular and extravascular spaces is vital for maintaining the body's homeostasis. However, disturbances in this delicate equilibrium, can lead to the clinical picture of CLS (Saravi et al., 2023).

CLI is measured by dividing CRP level by albumin level. Systematic response to tissue injury, including major surgery, is marked by increased pro inflammatory cytokines, which promotes CRP production and capillary leakage. If the injury still exists, inflammatory process will continue (Susanti et al., 2021).

Our study will be done to evaluate the association between capillary leak index (CLI) and intensive care unit (ICU) related mortality in patients underwent major abdominal surgery.

## **2. AIM/OBJECTIVES**

In this study we are going to evaluate the “CLI” as an early prognostic indicator for post-operative abdominal sepsis in critically ill patients.

### 3. METHODOLOGY:

#### Patients and Methods

➤ **Type of Study:** Prospective Cohort study.

➤ **Study Setting:** Surgical intensive Care Unit, Ain Shams University Hospitals.

➤ **Study Period:** 6 months.

➤ **Inclusion criteria:**

- Age:  $\geq 18$  years old presented with Post-operative intra-abdominal sepsis due to secondary peritonitis in the form of fever, increase TLC more than  $12 \times 10^3$  and increase procalcitonin  $> 0.5$  microgram per liter.
- Sex: Both sexes.
- Post-Operative secondary peritonitis eg. Perforated viscus and abdominal abscess.
- Estimated length of ICU stays  $\geq 48$  hrs.

➤ **Exclusion criteria:**

- Patient refusal.
- Advanced Liver diseases According New MELD score  $\geq 20$  (Kamath et al.,2001)
- Renal diseases (Moderate decrease in GFR 30-59 ml/min/1.73m^2--Severe decrease in GFR 15-29 ml/min/1.73m^2--Kidney failure less than 15 ml/min/1.73m^2 or on Hemodialysis).
- Pregnancy.
- Primary peritonitis.
- Tertiary peritonitis
- Mortality within first 48hrs of ICU admission.
- Advanced malignancy ( Stage III localized malignancy with spreading lymph nodes Stage IV spreading to Other parts of the body such as to the liver, lungs and bones)

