#### **Sampling Method:**

Simple randomization.

**Sample Size:** Using the PASS 15 program for sample size calculation, reviewing results from the previous study (Susanti et al, 2021) showed that the mortality rate among

the study group was 14.5%11/67) and, that the CLI at day three is a good predictor for mortality with ROC-AUC=0.892, based on these findings and after 15% adjustment for dropout rate a sample size of at least 50 patient achieves 95% power to detect a difference of 0.3920 between the area under the ROC curve (AUC) under the null hypothesis of 0.5000 and an AUC under the alternative hypothesis of 0.8920 using a two-sided z-test at a significance level of 0.050. The data are continuous responses.

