### **Study Procedures:**

All patients will be subjected to the following in the first post-operative day in the ICU:

1. Full history taking including

- Demographic Data: these include age, sex and BMI.
- Medical history: this includes diabetes mellitus (DM), cardiopulmonary diseases, renal or hepatic diseases.
- APACHE II Score.

- SOFA Score.
  2. Patients will be divided into two groups according to CLI
- Group I: Low CLI < 85.55
- Group II: High CLI > 85.55 (**PALACIOS et al., 2018**).

3. History of previous operations.
4. Drug history & special habits.
5. Complain of the patient:
  - Abdominal pain: This included onset, course, duration, site, radiation.
6. Associated symptoms: e.g.: Vomiting, change in bowel habits (constipation or diarrhea), Fever, tachycardia and tachypnea.
7. Investigations:
  - Laboratory investigations: Complete blood count (CBC). Liver function tests (LFT). Renal Function test (RFT). Coagulation profile. Daily assessment.
  - Specific laboratory investigations: CRP and Serum albumin Daily assessment.
  - Radiological investigations: Plain abdomen X-ray erect x-ray, Pelvi-abdominal ultrasonography, Computed Tomography (CT) abdomen as needed.
8. Management of sepsis and septic shock and will be done according to surviving sepsis campaign guidelines 2021.
9. Continuous monitoring of Temp, NIBP, IBP, HR, RR, intra-abdominal pressure, sPO2, UOP and GCS.

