### **Sampling:**

Blood sampling: About 5.0 ml venous blood sample was taken from each patient. 2.0 ml blood was put into vacutainer Ethylene-diaminetetra-acetic acid (EDTA) tube for CBC. The reminder of blood sample was put into plain tube for serum separation and estimation of LFT, RFT, The CRP level was measured using ABX Pentra 400 (HORIBA, Germany), whereas the albumin level was measured using HumaStar 80 (HUMAN, Germany). Reference values for serum albumin is 35 to 55 g/l and for CRP is less than 6 mg/dl CLI will be calculated as CRP divided by serum albumin and multiplied by 100 in the first day post-operative and daily for 5 days with a cut-off

point  $< 85.55$  (PALACIOS et al., 2018).

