## **Measurements**

### Primary outcome measure:

Correlation between CLI and 28 days Mortality.

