### Evaluation of Diagnostic Performance:

a) Diagnostic sensitivity: It measures the incidence of true positive results in patients' groups.  $(TP)/(TP+FN) \times 100$ . Where:

TP (true positive): number of diseased patients accurately classified by the test and FN (false negative): number of diseased patients accurately misclassified by the test.

b) Diagnostic specificity: It measures the incidence of true negative results in a non-diseased group.  $(TN)/(TN+FP) \times 100$ . Where:

TN (true negative): number of non-diseased subjects correctly classified by the test FP (false positive): number of non-diseased patients misclassified by the test.

c) Positive Predictive value (PPV): It is the percentage of true positive results among total positive results.  $(TP)/(TP+FP) \times 100$ .

d) Negative Predictive value (NPV): It is the percentage of true negative results among total negative results.  $(TN)/(TN+FN) \times 100$ .

e) Receiver Operating Characteristic curve (ROC-curve) analysis:

The overall diagnostic performance of each test was assessed by ROC curve analysis, a curve that extends from the lower left corner to the upper left corner then to the upper right corner is considered a perfect test. The area under the curve (AUC) evaluates the overall test performance (where the area under the curve >50% denotes acceptable performance and area about 100% is the best performance

for the test). A value below 0.5 indicates a very poor model. A value of 0.5 means that the model is no better than predicting an outcome than random chance. Values over 0.7 indicate a good model. Values over 0.8 indicate a strong model. A value of 1 means that the model perfectly predicts those group members who will experience a certain outcome and those who will not.

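### Deaths within 48 hours of ICU admission are excluded although they belong to the 28-day mortality outcome, so a day-1 CLI analysis is selected on its own outcome

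*Combined protocol and SAP*

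**What the plan says.** - Protocol, Patients and Methods, exclusion criteria: "Mortality within first 48hrs of ICU admission".
- Same section, inclusion criteria: "Estimated length of ICU stays" of at least 48 hours, a forecast made at entry.
- Protocol, Primary outcome measure: "Correlation between CLI and 28 days Mortality". The start of the 28 days is not defined.
- Protocol, Study Procedures: "All patients will be subjected to the following in the first post-operative day in the ICU". The list that follows includes "Patients will be divided into two groups according to CLI", with 85.55 as the dividing value.
- Protocol, Sampling: CLI is calculated "in the first day post-operative and daily for 5 days with a cut-off" of 85.55. The day used for the primary analysis is not named.
- Protocol, Sample Size: the planning result from the cited study is "that the CLI at day three is a good predictor for mortality with ROC-AUC=0.892".
- SAP, Evaluation of Diagnostic Performance: sensitivity, specificity, PPV, NPV and the ROC curve are to be reported. PPV is defined thus: "It is the percentage of true positive results among total positive results".

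Neither the protocol nor the SAP says how a patient who is measured on day 1 and dies before 48 hours is to be counted.

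**The concern.** Pregnancy, liver disease and the other exclusions can be checked at entry. Death within 48 hours cannot: it is a later event, and one of the events the study sets out to predict. Under Study Tools, consent comes before the assessments, and Study Procedures puts the CLI grouping on the first post-operative day. A patient can thus be enrolled, measured and grouped, and then be removed for dying. The inclusion criterion on expected ICU stay already deals with early deaths that can be foreseen, so what the exclusion adds is the removal of unforeseen ones.

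The stated aim is to use CLI as an early marker of prognosis. A clinician reading CLI on day 1 does not know who will survive 48 hours, so accuracy figures computed only in those who did would not describe the patients in front of that clinician. Since no count of early deaths is planned, a reader could not tell how many events had been taken out.

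**Working it through.** **The plan's own figure.** The sample size reproduces. For a one-sample AUC test of 0.892 against 0.5, two-sided 0.05, 95% power and 14.5% mortality with deaths rounded up, 42 evaluable patients with 7 deaths are needed, and 42/0.85 = 49.4, so 50. This matters here only for the scale of the event count: 50 × 0.145 = 7.25 expected deaths, or 50 × 11/67 = 8.2. The protocol prints both 14.5% and 11/67, and 11/67 is 16.4%.

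**Observed mortality.** Let m be true 28-day mortality and s the share of those deaths that fall within 48 hours. After deletion, observed mortality = m(1 − s)/(1 − ms). The documents do not give s; the values below are assumptions. They also assume that the cited mortality includes early deaths, which the documents do not state.

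| s (assumed) | m = 14.5% | m = 11/67 = 16.4% |
|---|---|---|
| 10% | 0.1305/0.9855 = 13.2% | 15.0% |
| 20% | 0.1160/0.9710 = 11.9% | 13.6% |
| 30% | 0.1015/0.9565 = 10.6% | 12.1% |

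**Sensitivity, PPV and NPV at 85.55.** Deleting early deaths removes only true positives (TP) or false negatives (FN); survivors are untouched, so specificity does not change. Losing a TP lowers PPV = TP/(TP + FP) and leaves NPV alone. Losing an FN raises NPV = TN/(TN + FN) and leaves PPV alone. These directions follow from the SAP's formulas. The counts below are assumed (50 patients, 7 deaths) and show scale only:

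| Data set | TP | FN | TN | FP | Sensitivity | PPV | NPV |
|---|---|---|---|---|---|---|---|
| All patients | 5 | 2 | 34 | 9 | 5/7 = 71.4% | 5/14 = 35.7% | 34/36 = 94.4% |
| One early death with high CLI deleted | 4 | 2 | 34 | 9 | 4/6 = 66.7% | 4/13 = 30.8% | 34/36 = 94.4% |
| One early death with low CLI deleted | 5 | 1 | 34 | 9 | 5/6 = 83.3% | 5/14 = 35.7% | 34/35 = 97.1% |

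One deleted death moves sensitivity by about −5 or +12 percentage points.

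**AUC.** Early and late deaths are compared with the same 28-day survivors, so AUC(all) = s × AUC(early) + (1 − s) × AUC(late) holds exactly. The analysis reports AUC(late), so its bias is s × [AUC(late) − AUC(early)]. With an assumed gap of 0.15:

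- Early 0.85, late 0.70: AUC in all patients is 0.715, 0.730 or 0.745 at s = 10%, 20% or 30%, against 0.70 reported (too low by 0.015, 0.030 or 0.045).
- Early 0.70, late 0.85: AUC in all patients is 0.835, 0.820 or 0.805, against 0.85 reported (too high by the same amounts).

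Neither the direction nor the size of the AUC bias can be found from the documents.

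**The case against.** The strongest reply is that the restriction acts as a landmark. Read with the 48-hour stay criterion, it defines a cohort of 48-hour survivors, and day 3 is the only CLI day tied to prognosis in the protocol. A day-3 CLI requires survival to day 3 anyway. For that analysis the point stands, and the only fault is that the landmark is not declared. But day 3 appears solely as the source of the planning AUC. No section makes it the index day, the CLI grouping is placed on day 1, and a population of 48-hour survivors cannot be recognised when a day-1 CLI is read.

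A second reply is that the clocks differ: the exclusion runs from ICU admission, CLI from the operation. A patient already in the ICU for 48 hours before the relevant operation would pass the criterion prospectively. That is possible but atypical for patients admitted after surgery, and the plan does not describe it.

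Third, the sizes rest on assumed inputs, and the expected-stay criterion may leave few early deaths, perhaps none. This is correct. If no measured patient dies within 48 hours, the results do not change.

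Finally, the SAP is written in the past tense, so eligibility may no longer be open to change. That limits how the repair is made; it does not remove the problem.

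**Conclusion.** The concern holds for any analysis of CLI measured before 48 hours. The plan states a rule that removes measured patients according to the primary outcome, and it declares no landmark that would justify this. If any such patient dies early, mortality is understated, PPV is unchanged or too low, NPV is unchanged or too high, and the AUC refers to later deaths only. The directions for mortality, PPV and NPV are certain given one such death. The size, and the direction of the AUC bias, are unknown because the documents give neither the share of early deaths nor how well CLI separates them. With seven or eight expected deaths, a single deletion is visible in the results. No loss of power is claimed: 0.892 is a day-3 AUC, and the plan does not say whether excluded patients are replaced. The change should be made, because the flaw is structural and the repair is cheap.

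**What to change.** 1. Remove death within 48 hours from the exclusion criteria. The entry criterion on expected ICU stay can remain.
2. In the day-1 analysis, keep every enrolled patient who has a day-1 CLI and count deaths within 48 hours as 28-day deaths. Report separately the number who died before the day-1 sample.
3. For later CLI values, such as day 3, declare a landmark: include only patients alive at that time and count deaths from then to day 28.
4. Report 48-hour survivors as a sensitivity analysis of the day-1 result, with the number of early deaths by CLI group.

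The plan should also say which CLI day is primary; the steps above work with either choice. If enrolment has closed, restore early deaths for whom a day-1 CLI was recorded, or at least report their number by CLI group.

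The cost is one protocol line and a short SAP paragraph. No further sampling is needed, since the patients kept already have a day-1 CRP and albumin. The small downside is that some moribund patients enter the day-1 analysis; the sensitivity analysis shows the result without them.

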#### **Sampling Method:**

Simple randomization.

**Sample Size:** Using the PASS 15 program for sample size calculation, reviewing results from the previous study (Susanti et al, 2021) showed that the mortality rate among

the study group was 14.5%11/67) and, that the CLI at day three is a good predictor for mortality with ROC-AUC=0.892, based on these findings and after 15% adjustment for dropout rate a sample size of at least 50 patient achieves 95% power to detect a difference of 0.3920 between the area under the ROC curve (AUC) under the null hypothesis of 0.5000 and an AUC under the alternative hypothesis of 0.8920 using a two-sided z-test at a significance level of 0.050. The data are continuous responses.

### **Ethical considerations:**

- An informed consent according to rules of ethical committee in Ain Shams University will be obtained from the patients or guardians after being informed about the research procedure and any potential risks suspected.
- All patients' data are highly confidential.

### **Study Tools:**

After an informed consent, the enrolled patients will be subjected to:

- Full clinical assessment and history taking.
- Laboratory investigations including random blood sugar, arterial blood gases (ABG), complete blood count (CBC), serum albumin and C reactive Protein “CRP”, liver function test, Kidney function test and procalcitonin.
- Imaging studies including Pelvi-abdominal U/S and Pelvi-abdominal multi-slice (CT) with or without contrast.
- Other investigations include Electrocardiogram (ECG), Echocardiography.

### **Study Procedures:**

All patients will be subjected to the following in the first post-operative day in the ICU:

1. Full history taking including

- Demographic Data: these include age, sex and BMI.
- Medical history: this includes diabetes mellitus (DM), cardiopulmonary diseases, renal or hepatic diseases.
- APACHE II Score.

- SOFA Score.
  2. Patients will be divided into two groups according to CLI
- Group I: Low CLI < 85.55
- Group II: High CLI > 85.55 (**PALACIOS et al., 2018**).

3. History of previous operations.
4. Drug history & special habits.
5. Complain of the patient:
  - Abdominal pain: This included onset, course, duration, site, radiation.
6. Associated symptoms: e.g.: Vomiting, change in bowel habits (constipation or diarrhea), Fever, tachycardia and tachypnea.
7. Investigations:
  - Laboratory investigations: Complete blood count (CBC). Liver function tests (LFT). Renal Function test (RFT). Coagulation profile. Daily assessment.
  - Specific laboratory investigations: CRP and Serum albumin Daily assessment.
  - Radiological investigations: Plain abdomen X-ray erect x-ray, Pelvi-abdominal ultrasonography, Computed Tomography (CT) abdomen as needed.
8. Management of sepsis and septic shock and will be done according to surviving sepsis campaign guidelines 2021.
9. Continuous monitoring of Temp, NIBP, IBP, HR, RR, intra-abdominal pressure, sPO2, UOP and GCS.

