### Secondary outcomes measure:

- Mechanical Ventilation days.
- Incidence of organ failure.
- Length of ICU stays.

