# Statistical analysis Plan

## NCT Number: NCT06901544

Statistical analysis was done by SPSS v27 (IBM©, Armonk, NY, USA). Shapiro-Wilks test and histograms were used to evaluate the normality of the distribution of data. Quantitative parametric data were presented as mean and standard deviation (SD) and were analyzed by unpaired student t-test. Quantitative non-parametric data were presented as the median and interquartile range (IQR) and were analyzed by Mann Whitney-test. Qualitative variables were presented as frequency and percentage (%) and analyzed using the Chi-square test. A two-tailed P value < 0.05 was considered statistically significant.

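### On the natural reading, ventilation days, ICU stay and organ failure are compared only between low and high CLI groups; a continuous-CLI analysis would keep information that the 85.55 split discards

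*Combined protocol and SAP*

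**What the plan says.** Study Procedures, item 2, says "Patients will be divided into two groups according to CLI" and defines them as "Group I: Low CLI < 85.55" and "Group II: High CLI > 85.55". The cut-off is cited from a published study in septic shock. A value of exactly 85.55 belongs to neither group.

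The primary outcome is "Correlation between CLI and 28 days Mortality". The secondary outcomes are "Mechanical Ventilation days", "Incidence of organ failure" and "Length of ICU stays".

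The Statistical Analysis Plan gives an unpaired t-test for normally distributed quantities, says that the others "were analyzed by Mann Whitney-test", and gives chi-square for categorical variables. It does not say which groups are compared or which test serves which outcome. The protocol's own Statistical Analysis section adds nothing specific. No correlation coefficient or regression model is named anywhere.

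The SAP section on diagnostic performance adds sensitivity, specificity, predictive values and ROC/AUC analysis. The Sample Size section is built on an AUC of 0.892 against 0.5 and treats the data as continuous.

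**The concern.** CLI is a continuous marker, calculated from CRP and albumin that are measured in every patient. Cutting it at one value treats all patients on the same side as alike, and treats two patients just either side of 85.55 as different. ROC analysis avoids this for death. As the SAP describes it, however, ROC analysis needs a yes/no outcome, so it cannot serve ventilation days or ICU stay, and the SAP does not apply it to organ failure.

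The low/high CLI groups are the only patient groups that the protocol defines. If the two-group tests compare those groups, the three secondary outcomes get the weaker analysis in a study of about 50 patients. How much is lost depends on how evenly 85.55 divides this population, which the documents do not say. The cut-off comes from a different population, so an uneven split is possible.

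**Working it through.** **1. The plan's own figure.** Inputs from Sample Size: AUC 0.892 against 0.5, two-sided alpha 0.05, power 95%, mortality 14.5%, dropout 15%. (The fraction printed beside the mortality rate, 11/67, is 16.4%; 11/76 would be 14.5%.) Power = Φ[(0.392 − 1.96·SE₀)/SE₁].
- Hanley-McNeil standard errors: 44 evaluable; 44/0.85 = 51.8, so 52.
- Obuchowski standard errors: 43 evaluable; 43/0.85 = 50.6, so 51, or 43 × 1.15 = 49.5, so 50.

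The stated 50 reproduces to within 2 patients. The calculation uses ungrouped CLI, so the split costs this analysis nothing.

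**2. Information kept by a split.** For a normal predictor (here log-CLI) with a linear effect, cut so that a share q lies above the cut-point c, the information retained is φ(c)²/[q(1 − q)]:
- 50/50: 0.3989²/0.25 = 0.64
- 80/20: 0.2800²/0.16 = 0.49
- 90/10: 0.1755²/0.09 = 0.34

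| Split | Retained | Effective size of 50 | Size needed to match 50 with continuous CLI |
|---|---|---|---|
| 50/50 | 64% | 32 | 79 |
| 80/20 | 49% | 25 | 103 |
| 90/10 | 34% | 17 | 147 |

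**3. Sensitivity to the distribution.** For a linear effect and a median split, a uniform CLI loses 25%, an exponential CLI 52% and a lognormal CLI (sigma 1, effect linear on the raw scale) 73%. The documents give neither the distribution nor the share above 85.55.

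The share also depends on units. The Sampling section gives reference values in mg/dl for CRP and g/l for albumin, but no unit for CLI. At albumin 35 g/l, the cut-off corresponds to a CRP of 85.55 × 35/100 = 29.9. Whether that is in mg/dl or mg/l moves the cut tenfold. A constant unit factor changes neither a rank correlation nor a slope on log-CLI.

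**4. Power for a quantitative secondary outcome.** The documents give no effect size, so a correlation of 0.4 is assumed. Simulation used bivariate normal data, 4,000 replicates and two-sided 0.05, comparing Spearman on continuous CLI with Mann-Whitney on the split.

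| n | Spearman | Split 50/50 | Split 80/20 | Split 90/10 |
|---|---|---|---|---|
| 50 | 79% | 61% | 47% | 34% |
| 42 | 71% | 53% | 41% | 30% |

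(50 × 0.85 = 42.5 patients after the planned dropout.) A repeat run agreed to within about 2 percentage points.

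A closed-form check by Fisher's z, for n = 50:
- Continuous: 0.4236 × √47 − 1.96 = 0.94, so power is 83%.
- 50/50 split: the correlation falls to 0.4 × √0.637 = 0.319; 0.3307 × √47 − 1.96 = 0.31, so power is 62%.

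Over a range of assumed correlations, the same formula gives:
- 0.3: 56% continuous, against 39% (50/50) and 31% (80/20).
- 0.5: 96% continuous, against 82% (50/50) and 71% (80/20).

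**5. Deaths available for a mortality model.** 50 × 0.145 = 7.25, so about 7.

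**The case against.** The strongest reply is that the relation of CLI to death, which is the primary question and the one the study was sized for, is already analysed with continuous CLI. This stands. A reader might infer that the primary outcome has no continuous-CLI analysis, or that the whole study throws away a third or more of its information. The documents support neither. For a binary outcome, 2 × AUC − 1 is a rank correlation: at the planning value, 2 × 0.892 − 1 = 0.784. The AUC therefore answers to the word correlation in the primary outcome. What it does not give is an odds ratio per unit of CLI. That would be a useful supplement, but its absence does not leave the primary analysis missing.

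Second, the SAP does not name its groups. It could mean survivors against non-survivors, or patients with against without organ failure. CLI would then be the continuous variable under test and nothing would be lost in those comparisons. This also stands, so the grouping is an inference. But that reading would leave the relation of CLI to ventilation days and ICU stay with no planned analysis, so the SAP needs the same addition.

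Third, a reader might conclude that real associations will probably be missed. The figures do not show that in general: at a correlation of 0.4 and an even split, power is still 61% with 50 patients and 53% with 42. It falls below half at the uneven splits, which are assumptions.

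**Conclusion.** The point holds for the three secondary outcomes and does not touch the AUC for 28-day mortality. On the natural reading of the plan, these outcomes are analysed by a method that keeps 64% of the information at best if log-CLI is normal with a linear effect, and 34% if only one patient in ten falls on one side of 85.55. Under a uniform CLI cut at its median the loss would be nearer 25%, so a loss of a third is not a floor. At an assumed correlation of 0.4 with 50 patients, the cost is about 18 percentage points of power at an even split (79% − 61%) and 45 at 90/10 (79% − 34%). These sizes rest on the assumed distribution, split share and correlation, none of which is in the documents. That the SAP names no groups, no test per outcome, and no regression or correlation coefficient is plain from the text.

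**What to change.** - State in the SAP which analysis serves each outcome and which groups each two-group test compares. Say on which side a CLI of exactly 85.55 falls.
- Keep the 85.55 groups for description and for sensitivity and specificity.
- Make continuous CLI from one pre-named day the main secondary analysis. CLI is calculated daily over 5 days, the grouping sits among the first post-operative day procedures, and the planning AUC is for day three, so the day must be fixed in advance; post-operative day 1 is one option.
- For ventilation days and ICU stay, use Spearman correlation with a stated rule for deaths. Death shortens both, so if high CLI predicts death, a correlation on raw days can be pulled towards zero or reversed. Options are to rank deaths as the worst outcome, or to report survivors only as an additional analysis.
- For organ failure, use logistic regression on log-CLI.
- Optionally, beside the AUC, report a Firth-penalised odds ratio for 28-day death per doubling of CLI with a 95% confidence interval. CLI should be the only predictor. About 7 expected deaths will make the estimate imprecise, and the report should say so.

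The cost is SAP wording and slightly more analysis work, on measurements that are already planned. The statistical downside is an assumed log-linear form in the logistic models; Spearman does not need it.
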